3.7 Subjects Coding

At the time of enrollment, each subject will be assigned a complex alphanumeric identification code formed by the progressive enrollment number followed by an alphanumeric code generated by GUNA S.p.a. through Random Sequence Generator (www.random.org).

The complex code is found to be in compliance with the current Privacy Regulations regarding coding of subjects participating in clinical trials.

4.9 Procedures

4.9.1 Timing of Evaluation

T0 baseline: Enrollment and start of infiltrative treatment.

T2 weeks: Second infiltrative treatment.

T4 weeks: Third infiltrative treatment.

T3 months: Visit 1st Evaluation.

T6 months/FU: Follow-up visit.

T12 months/FU: Follow-up visit.

4.9.2 Plan Visits

T0 BASAL: Enrollment

During the daily clinical activity, investigators participating in the Investigation will select subjects with rotator cuff syndrome. The Principal Investigator will be responsible for the correct clinical diagnosis by also making use of the instrumental examinations provided in the Investigation Plan. Subjects meeting the selection criteria will thus be identified. After fully explaining the purposes, aims and procedures stipulated in the Clinical Investigation Plan, the subject will be offered participation in the Clinical Investigation Plan itself. Finally, the selected subject will be asked to review the information form and to date and sign the Informed Consent and Consent to Processing of Personal Data form.

Female subjects will need to provide evidence of a negative pregnancy test in order to be enrolled.

We will then proceed with the objective examination and collection of the information required by the appropriately prepared Electronic Data Collection Form.

This will be followed by:

- CMS assessment;
- NRS assessment;
- ASES assessment.
- SST evaluation;
- shoulder ROM evaluation;
- MRI evaluation.

The first infiltration will then be performed via ultrasound.

Previous or ongoing pharmacological treatments of any kind will be documented.

In order to monitor the consumption of analgesic (Celecoxib 200mg / Paracetamol 1000 mg) used during the Clinical study in case of pain onset, a clinical diary will be given to the subject in which to indicate the day and dose of medication used.

The enrolled subject will be given the identification code formed by the progressive enrollment number followed by an alphanumeric code.

T2 week (±2 days):

At 14 days from day 0 (enrollment), the second infiltration will be performed through echoguide and pain assessment through NRS, finally painkiller drug use will be evaluated through clinical diary analysis, and any Adverse Events occurred after the first administration will be assessed.

T4 weeks (±2 days):

At 28 days from day 0 (T4w), the third ultrasound-guided infiltration and pain assessment through NRS will be performed, finally painkiller drug use will be assessed through clinical diary analysis and any Adverse Events occurred after the last administration will be evaluated.

T3 months (±7 days):

At 3 months from day 0 and at 2 months from the last echoguided administration, the End Points in the Clinical Investigation Plan will be assessed.

Including:

- CMS assessment;
- NRS assessment;
- ASES assessment.
- SST assessment;
- shoulder ROM assessment;
- assessment of pain killer drug consumption used in case of pain onset through clinical diary;
- evaluation of any Adverse Events.

T6/FU (±7days):

At 6 months from day 0, we will again proceed with the assessment of the End Points stipulated in the Clinical Investigation Plan.

Including:

- CMS assessment;
- NRS assessment;
- ASES assessment.
- SST assessment;
- shoulder ROM assessment;
- assessment of painkiller drug consumption used in case of pain onset

- through clinical diary;
- evaluation of any Adverse Events.

T12/FU(±7days):

At 12 months from day 0, i.e at the end of the Clinical Investigation, all the End Points set out in the Investigation Plan will be re-assessed.

Including:

- CMS assessment;
- NRS assessment;
- ASES assessment.
- SST assessment;
- shoulder ROM evaluation;
- MRI assessment;
- painkiller drug consumption assessment used in case of pain onset

through clinical diary;

- evaluation of any Adverse Events;

Diagnosis, evaluation of inflammatory and degenerative signs at MRI investigation of the shoulder with rotator cuff syndrome will be performed by the Principal Investigator.

The CMS, ASES, SST rating scales will be administered to the subject by the Co-Investigator. Recording of the clinical diary data regarding painkiller medication intake will be performed by the Co-Investigator.

The occurrence of Adverse Events will be assessed at each visit. All Adverse Events (AEs), Serious Adverse Events (SAEs) and Suspected Serious and Unexpected Adverse Reactions (SUSARs) occurring between the date of signing the Informed Consent and the end of the Clinical Investigation will be recorded and reported.

All data collected will have to be entered by the Data Manager in the Electronic Data Collection Form (e-CRF) provided by Guna S.p.a. The Principal Investigator and the Data Manager identified by him will be responsible for the correct entry of the collected data in the e-CRF.

In particular, it is planned to obtain a data collection that is schematically described in the following table (Tab. 1), which shows the entries to be made at each visit:

EXPERIMENTAL PROCEDURES	VISIT T0 Enrollment	VISIT T2weeks ± 2days	VISIT T4weeks ± 2days	VISIT T3 months ± 7days	VISIT T6/FU ± 7days	VISIT T12/FU ± 7days
Diagnosi clinica RCS	X					
Valutazione criteri di selezione	X					
Signing Informat consent	X					
Signing of privacy agreement	X					
Socio-demographic data collection	X					
Anamnestic collection	X					
NRS Assessment	X	X	X	X	X	X
CMS Assessment	X			X	X	X
ASES Assessment	X			X	X	X
SST Assessment	X			X	X	X
Shoulder ROM assessment	X			X	X	X
MR Assesment	X					X
Infiltrative Treatment	X	X	X			
Evaluation of clinical diary analgesic consumption.	X	X	X	X	X	X
Evaluation of clinical diary concomitant treatment for ongoing co-morbidities	X	X	X	X	X	X
Adverse Event Evaluation (AE/SAE)	X	X	X	X	X	X

Tab.1 Data collection during the clinical Investigation

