3.5 Participating population

A total of 24 subjects with painful shoulder in rotator cuff tendinopathy will be enrolled. The recruitment phase will be closed no earlier than the number of subjects stipulated in the Clinical Investigation Plan has been reached.

Only subjects will be included:

- belonging to the U.O.C. 1st Orthopedic Clinic (Gaetano Pini Orthopedic Institute, Milan, Italy);
- who meet the inclusion criteria and have no exclusion criteria.

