4.11 Study group

Only one experimental group is included in the investigation plan, which will be treated with 2 ml volume ultrasound-guided infiltrations of MD-Shoulder *Collagen Medical Device* (GUNA, Milan-Italy). Composition per 2 ml: collagen 100 micrograms.

Excipients: Iris, NaCl, Water for injection. Subjects will be treated with no. 1 ultrasound infiltration at the time of enrolment, 2 weeks after enrolment and 4 weeks after enrolment.

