5 STATISTICS

5.1 Sample size

This is a one-sample study. We assume that at baseline the expected mean value of the Constant-Murley score is 65.0 and that given the eligibility criteria this value is between 50 and 80, we can therefore estimate the mean value to be 65.0 ± 7.5 .

It is also expected, that at the end of the treatment i.e. at months 3, using the alternative hypothesis $H_a: \Delta = 13$, compared to the null hypothesis $H_0: \Delta = 0$, estimating that the standard deviation of the differences is $s_{diff} \leq 20$. With these assumptions a sample of 24 patients has a power of 86.2% in discriminating a difference of 13 with a standard deviation of the differences of 20, if a Student's t-test for paired data is used. If the data were not Gaussian distributed, instead of using the nonparametric equivalent (Wilcoxon test, where the power would still be at least 82,8%), we would prefer - if possible - to use a non-linear transformation of the data.

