5.2.2 Primary Endpoint

The primary endpoint will be assessed by Student's t-test for paired data as already established in the section on sample size.

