6.4 Adverse Events

An Adverse Event is defined as any harmful clinical event that will occur during the course of the clinical investigation in one of the subjects comprising the study population who has undergone one of the treatments in the investigation plan.

Adverse events will be classified into serious (SAE) non-serious (AE) and Suspected Serious and Unexpected Adverse Reactions (SUSAR).

An Adverse Event is defined as serious if (ICH-GCP DM 15/07/1997):

- it causes the death of the subject involved in the investigation
- places the subject's life in danger
- is such as to require hospitalization
- is such as to require prolonged hospitalization
- is such as to cause permanent or temporary disability
- leads to a congenital anomaly or birth defect

In all other cases, the Adverse Event will be non-serious and will be classified as:

- *mild* does not interfere with normal activities of daily living and resolves spontaneously.

- *moderate*, interferes with activities of daily living but resolves spontaneously;
- *severe*, prevents daily life activities and does not resolve spontaneously.

All personnel who come in contact with study subjects must report Adverse Events reported by subjects to the Investigator, who has a duty to collect all possible data about them.

- Adverse events (AEs) will be reported within 48 h by the Principal Investigator to the Clinical Research Unit of Guna S.p.a, through telephone, email, appropriate form and simultaneously through e-CRF.
- Serious Adverse Events (SAEs) and Suspected Serious and Unexpected Adverse Reactions (SUSARs) will have to be reported to the Sponsor immediately (within 24 h maximum) through telephone, email, appropriate form and simultaneously through e-CRF by the Principal Investigator and communicated to the Ethics Committee and the Ministry of Health.

Unità di Ricerca Clinica di GUNA S.p.a.

[contact]

mail: [contact]

[contact]

[contact]

Ufficio Farmacovigilanza di GUNA S.p.a.

[contact]

mail: [contact]

[contact]

The investigator should ensure that procedures are in place to ensure that the event is resolved.

In the case of nonserious Adverse Events (AEs), it is necessary to keep in mind that they can still give rise to serious events, which is why each Adverse Event must be monitored.

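### The third infiltration has no scheduled adverse event enquiry for about two months, and the diary as described has no place for events, so mild reactions after it may be under-recorded

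*Combined protocol and SAP*

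**What the plan says.** - **Treatment times.** Section 4.11 gives one infiltration "at the time of enrolment, 2 weeks after enrolment and 4 weeks after enrolment".
- **AE enquiries.** Section 4.9.2 states: "The occurrence of Adverse Events will be assessed at each visit". Tab. 1 marks AE evaluation at all six visits (day 0, weeks 2 and 4, months 3, 6 and 12). Neither lists a contact between visits.
- **What each enquiry covers.** In section 4.9.2 the week 2 visit asks about events after the first administration. The week 4 visit asks about events after the last one. Infiltration 3 is given at that same week 4 visit, so the interval reviewed there is the one after infiltration 2. The 3-month visit is placed "At 3 months from day 0 and at 2 months from the last echoguided administration".
- **Diary.** For analgesic use, section 4.9.2 says "a clinical diary will be given to the subject in which to indicate the day and dose of medication used". Tab. 1 adds concomitant treatment for co-morbidities. The form is listed as Attachment C in section 8, but it is not in the text available for this review.
- **Other routes.** Section 4.9.2 requires all AEs from consent to study end to be recorded. Section 6.4 obliges staff to pass on any AE that a subject reports, and sets a reporting time: "Adverse events (AEs) will be reported within 48 h by the Principal Investigator". Scheduled monthly contact appears only after the study ends, for subjects who have had an AE.
- **Role of safety.** It is in the title and the purpose (sections 3.1 and 3.2). AEs are listed among the secondary endpoints (sections 4.13.3 and 5.2.3).

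**The concern.** The course of three infiltrations is complete at week 4, yet the last one has the weakest follow-up for early reactions. By the grading in section 6.4, mild and moderate events clear up without intervention. Such an event in the days after infiltration 3 may leave no sign by month 3. Whether it is recorded then depends on the subject volunteering it or remembering it about two months later.

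This matters more than it would in a controlled trial. There is one arm of 24 subjects and no comparator with the same ascertainment, so the AE record itself is the safety result. Because the enquiry interval also differs between infiltrations, AE counts by infiltration could not be compared directly.

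**Working it through.** **Inputs**
- Infiltrations at day 0, day 14 ± 2 and day 28 ± 2 (section 4.9.2).
- Later visits at months 3, 6 and 12, each ± 7 days (section 4.9.2).
- 24 subjects (section 3.5), one arm (section 4.11).
- Assumption: 1 month = 30.44 days, so months 3, 6 and 12 fall at about days 91, 183 and 365.

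**The plan's own figure.** From infiltration 3 to the 3-month visit is 91.3 − 28 = 63.3 days, and 63.3 / 30.44 = 2.1 months. This agrees with the two months stated in section 4.9.2.

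**Days from each enquiry or infiltration to the next enquiry.** The nominal gap is the difference between the two target days. The range subtracts and adds both visit windows.

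| Interval | Nominal | Range |
|---|---|---|
| Infiltration 1 to week 2 | 14 | 14 ± 2 = 12 to 16 |
| Infiltration 2 to week 4 | 28 − 14 = 14 | 14 ± 4 = 10 to 18 |
| Infiltration 3 to month 3 | 91 − 28 = 63 | 63 ± 9 = 54 to 72 |
| Month 3 to month 6 | 91 | 91 ± 14 = 77 to 105 |
| Month 6 to month 12 | 183 | 183 ± 14 = 169 to 197 |

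The nominal interval after infiltration 3 is 63 / 14 = 4.5 times that after each of the first two.

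**Share of exposure affected.** Planned infiltrations are 24 × 3 = 72. Those without an early enquiry are 24 × 1 = 24, or one third. The other 48 have an enquiry at about 14 days.

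**Possible size, on assumed values only.** Suppose the reaction risk is equal at each infiltration, every reaction to infiltrations 1 and 2 is recorded, and a fraction c of those to infiltration 3 is recorded. The overall share recorded is (1 + 1 + c) / 3.

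| c (assumed) | Share recorded overall |
|---|---|
| 0.90 | 2.90 / 3 = 97% |
| 0.75 | 2.75 / 3 = 92% |
| 0.50 | 2.50 / 3 = 83% |
| 0.25 | 2.25 / 3 = 75% |

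The documents support no particular value of c. The table shows only how far the overall record could move.

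**The case against.** The strongest reply is that AEs are asked about at all six visits, that the plan does not contradict itself, and that for a single-arm post-market pilot this is a matter of preference. Several safeguards exist. All AEs from consent onward must be recorded, staff must pass on what subjects tell them, and month 3 asks retrospectively. Dated analgesic entries may also prompt memory of a painful reaction that was treated. These points stand and limit the size of the problem. They do not replace asking: spontaneous reports are passive, and medication entries miss untreated symptoms.

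A reader might infer more than the documents support:

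- **That reactions will be under-counted and the safety statement will be too favourable.** No event or recall rate is given, so only a possible shortfall can be claimed.
- **That the diary holds analgesics only, or certainly has no event field.** Tab. 1 shows it also covers co-morbidity treatment. Attachment C and the consent text could not be seen, so an event field or an instruction to contact the site cannot be ruled out.
- **That the three- and six-month gaps cause the same harm.** They begin about two and five months after the last infiltration and matter little for short-lived injection reactions.
- **That AEs will appear to fall after the third infiltration.** The plan has no analysis of AEs by infiltration. The longer interval could also collect more unrelated events, so the direction is not established.
- **That the 48 h reporting rule would be broken.** Section 6.4 does not say when the 48 h starts. Any visit-based collection learns late of mild events that nobody volunteers.

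**Conclusion.** The point holds in a limited form. No AE enquiry is scheduled for about 54-72 days after infiltration 3, against 12-16 and 10-18 days after the first two. The diary, as the text and Tab. 1 describe it, records medication and not symptoms or events. Mild, self-resolving reactions may be under-recorded, mainly after the third infiltration, which is one third of planned infiltrations. How many would be missed cannot be derived from the documents.

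The conclusion rests on the visit schedule as written and on Attachment C and the consent text not already providing for event capture. If the diary form does have an event field, the text and Tab. 1 should say so, and the missing early enquiry after infiltration 3 would remain. This is a cheap improvement to a stated objective, not a flaw that undermines the trial. Confidence is moderate.

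**What to change.** 1. In section 4.9.2 and Tab. 1, add one scheduled phone AE enquiry about 14 days after infiltration 3, made by the existing investigators.
2. Add a dated event or symptom field to the subject diary (Attachment C), if the form does not already have one. State in section 4.9.2 and Tab. 1 that it is reviewed at every visit.
3. If AEs are summarised by infiltration, count them by onset date from each infiltration to the earlier of day 14 or the next infiltration, and report later events separately. This rule is needed because the phone call alone does not equalise the windows: the next infiltration can come 12-16 days after the first and 10-18 days after the second. Under the rule the windows are 12-14, 10-14 and 14 days, so days at risk should be shown beside the counts.

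The cost is 24 × 1 = 24 short calls, one diary field, slightly more patient burden and probably a higher recorded AE count. Treatment, efficacy endpoints, sample size and power do not change.

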2.2 Tendinopathy and rotator cuff injuries

Rotator cuff tendinopathy is a commonly encountered musculoskeletal disorder in clinical practice, with an incidence ranging from 0.3% to 5.5%, and an annual prevalence of 0.5% to 7.4% [4]. Furthermore, over time, at a monthly rate of 0.26%, this condition can progress to complete rotator cuff tendon injury resulting in worsening pain and shoulder function [5].

The etiology of rotator cuff tendinopathy is still controversial. Some authors believe that it is an expression of a primary extrinsic compression due to a reduction of the sub-acromial space, while others attribute this pathology to an intrinsic degeneration of the tendons with a consequent development of secondary impingement. In this case, the hypothesis is that an altered microcirculation of the shoulder tendons leads to weakness of the rotator cuff resulting in rising humeral head and compression of the overlying structures. What we do know is that in tendinopathies there are histologic changes in the structure of the tendons, which include increased glycosaminoglycans and proteoglycans content, remodeling of collagen fibers, hypercellularity, neovascularization, and changes in the extracellular matrix pattern with increased noncollagenous components. These cellular

and molecular alterations result in a change in the mechanical properties of tendons and lead to a chronic, often disabling pain condition [6].

Although conservative therapy should still be considered the first choice in cuff tendinopathy, the clinical results of the various types of nonsurgical treatments are still mixed and often show poor efficacy.

Numerous studies identify exercise as the most viable therapeutic option in the treatment of rotator cuff tendinopathy, although the amount and type of potentially optimal exercise has not yet been defined. In addition, physiotherapy does not seem to be able to change the natural history of this pathology.

This explains the growing interest of the scientific community in developing new biological therapies that can both improve shoulder function and promote tendon healing.

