3.6 Enrollment

Enrollment will begin only after approval of the Clinical Investigation Plan by the ASST Istituto Ortopedico Gaetano Pini Ethics Committee and notification of the study at the Ministry of Health.

Enrollment will involve subjects with rotator cuff syndrome who are eligible according to the selection criteria. Diagnosis will be performed by the Principal Investigator through clinical examination and instrumental investigation with shoulder MRI. The MRI examination must be recent and of good quality; if the subject does not have it, an MRI examination will be performed before diagnosis and enrollment. Eligible subjects will be explained by the Co-Investigator the rationale for the Clinical Investigation Plan and the procedures involved. Consent to participate in the study will then be sought.

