4.13.3 Secondary End Points

The Secondary Endpoints will consist of evaluating the performance of MD-Shoulder *Collagen Medical Device* through:

- CMS at months 3, 6 and months 12 compared to day 0.
- NRS at week 2, week 4, months 3, months 6, months 12 compared to day 0
- ASES, SST and ROM at months 3, months 6, months 12 compared to day 0
- cuff integrity at months 12 compared to day 0 by performing MRI of the treated shoulder
- analgesic consumption at various phases of the study.
- evaluation of Adverse Events.

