4.14 Data collection

All data resulting from the Clinical Investigation will be entered, within seven days of their collection, into the electronic Data Collection Form (e-CRF) "Pheedit Dedagroup" provided by the Sponsor. Radiological data will be collected and stored digitally on the PACS system. Data entry procedures will be performed by the Data Manager.

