5.2.3 Secondary End Points

Secondary End Points will consist of evaluating the efficacy, in terms of performance, of MD-Shoulder *Collagen Medical Device* through:

- CMS at months 3, 6 and months 12 compared to day 0, using ANOVA with repeated measures within patient, or Friedman's test.
- NRS at week 2, week 4, months 3, months 6, months 12 compared to day 0 using ANOVA with repeated measures within patient, or Friedman's test.
- ASES and SST at day 0, months 3, months 6 and months 12 using ANOVA with repeated measures within patient, or Friedman's test.

- cuff integrity at day 0 and months 12 by performing MRI of the treated shoulder using Clopper-Pearson binomial test.
- analgesic consumption in the various phases of the study, understood as dosage units/month and evaluated as mean, CI 95% of mean, median, CI 95% of median, SD and range.
- adverse events by records of the various AEs, SAEs, SUSARs according to § 6.4.

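### Nothing in the plan hides the time point when the Principal Investigator's day-0 and month-12 MRI readings are compared for the secondary cuff-integrity endpoint; a masked re-read from the stored images would reduce the risk of tilted readings

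*Combined protocol and SAP*

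**What the plan says.** - **Reader.** Section 4.9.2, just after the list of month-12 assessments: "evaluation of inflammatory and degenerative signs at MRI investigation of the shoulder with rotator cuff syndrome will be performed by the Principal Investigator". No radiologist, second reader or central reader is named anywhere.
- **Baseline scan.** Section 3.6: "Diagnosis will be performed by the Principal Investigator through clinical examination and instrumental investigation with shoulder MRI". A recent scan that the patient already has may serve; otherwise one is made before enrolment.
- **Schedule.** Table 1 in section 4.9.2 places MRI at T0 and T12 only.
- **Endpoint.** Section 4.13.3 lists "cuff integrity at months 12 compared to day 0 by performing MRI of the treated shoulder" among the secondary endpoints. Section 5.2.3 gives the analysis: "cuff integrity at day 0 and months 12 by performing MRI of the treated shoulder using Clopper-Pearson binomial test".
- **Design.** Section 4.11: "Only one experimental group is included in the investigation plan".
- **Images.** Section 4.14: "Radiological data will be collected and stored digitally on the PACS system".
- **Other assessments.** Section 4.9.2 gives the CMS, ASES and SST scales and the recording of the analgesic diary to the Co-Investigator.

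The plan does not mention masking to time point, reading order, reader agreement or a grading scale for cuff integrity at either time point.

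**The concern.** Judging tendon signs on MRI involves discretion, and this endpoint is a within-patient comparison of two such judgements. The first is made before treatment, to decide whether the patient qualifies. The second belongs to the end-of-study visit. With one treated group, to know that a scan is from month 12 is to know that it is post-treatment. A reader who expects the device to help may, without intending it, settle borderline scans as improved or as not progressed.

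Treatment cannot be masked in a single-arm study, but the order of two stored images can. The final report is meant to reach reliable conclusions on efficacy and go to a journal (section 6.7), so the MRI result may be offered as structural support for the clinical scores. It would carry more weight if it had been read without the date.

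**Working it through.** **1. Is there a figure in the plan to reproduce?** Not for MRI. The only power figure, 86.2% in section 5.1, concerns the paired t-test on the CMS. With df = 23, non-centrality 13/20 × √24 = 3.18 and two-sided alpha 0.05 (assumed, since alpha is not stated), the noncentral t gives 86.2%. It reproduces, and a change in how scans are read does not touch it.

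**2. What the reader knows.**

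| Scan | What the documents give | Status |
|---|---|---|
| Day 0 | Used by the Principal Investigator to diagnose before the first infiltration (3.6, 4.9.2) | Time point known: documented |
| Month 12 | Part of the last visit; evaluated by the Principal Investigator; no step hides the date (4.9.2) | Time point known: inferred from the setting and the absence of masking |

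**3. Weight of one reading.** Input: 24 patients (sections 3.5 and 5.1), all assumed to have both scans.

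- 1/24 = 4.2 percentage points. If patients leave early (section 4.15), each reading weighs more; with 20 complete pairs, as an assumed example, 1/20 = 5.0 points.
- Section 5.2.3 names Clopper-Pearson but not the proportion. Taking it, as an assumption, to be the proportion read as progressed, the 95% limits are:
  - 0/24: lower 0; upper 1 − 0.025^(1/24) = 14.2%.
  - 1/24: lower, the 0.025 quantile of Beta(1, 24) = 0.1%; upper, the 0.975 quantile of Beta(2, 23) = 21.1%.
- One reading therefore moves the upper limit by 21.1 − 14.2 = 6.9 points.

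**4. Illustration for improvement.** The plan specifies no test of change for this endpoint, so an exact two-sided sign test is assumed. Six patients read as better and none as worse give p = 2 × 0.5^6 = 0.031; five give 2 × 0.5^5 = 0.063.

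Now suppose there is no true change and that 20% to 40% of patients are scored differently at month 12 through reading variability alone. The table gives the chance of a falsely significant improvement among 24 patients:

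| Share of differences that go towards improvement | 20% scored differently | 40% scored differently |
|---|---|---|
| 50% (no lean) | 0.4% | 1.1% |
| 70% | 3.6% | 14.2% |
| 80% | 8.6% | 34.6% |

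These rates are assumptions. They show the direction and sensitivity of the problem and do not estimate the bias in this trial.

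**5. Workload of a re-read.** 24 patients × 2 scans = 48 readings at most.

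**The case against.** The case against making much of this is a good one, and several parts of it stand.

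- **Awareness at month 12.** A reader might take it as documented that the investigator knows the date of both scans. It is documented for day 0 only; for month 12 it is a reasonable inference from silence.
- **Knowledge of outcomes.** A reader might also infer that the investigator reads the scan knowing how the patient has fared. The documents do not establish this. The Co-Investigator administers the CMS, ASES and SST and records the diary. The Principal Investigator answers for correct e-CRF entry (4.9.2) and reports adverse events (6.4), so could learn the outcome, but no section says that this happens before the scan is read.
- **Same reading?** The sentence in 4.9.2 speaks of inflammatory and degenerative signs, the endpoint of cuff integrity. Treating them as one evaluation is plausible because no other reader is named, but it is a step.
- **Using the background rate as a yardstick.** Section 2.2 says that "at a monthly rate of 0.26%, this condition can progress to complete rotator cuff tendon injury". It is tempting to compute 24 × (1 − 0.9974^12) = 0.74 expected progressions and conclude that one or two lenient readings equal the whole signal. The arithmetic is right but the inference is not supported. The rate concerns complete injury, while cuff integrity is undefined and patients with tendinopathy or subacromial conflict are also enrolled. It describes worsening, so it does not measure a lean towards improvement. Even if the rate applied, the chance of no progression at all would be 0.9974^(12 × 24) = 47%, leaving nothing to hide.
- **Imprecision.** A 4.2-point shift is small beside intervals 14 to 21 points wide. That is true, but the interval reflects sampling error only and does not allow for a systematic lean.
- **Importance.** This is one of several secondary endpoints in an uncontrolled pilot.

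What remains is that no section provides masking or a random reading order, and the stored images make both possible.

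**Conclusion.** The point holds as a modest, optional improvement. The plan lets a known time point influence the cuff-integrity reading: the day-0 reading is necessarily unmasked, and nothing hides the date of the month-12 scan. The tilt, if any, would be towards improvement or no progression. Its size cannot be computed from the documents; what can be said is that each changed reading counts for 4.2 percentage points when all 24 patients have both scans.

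The conclusion rests on two assumptions: that the MRI evaluation in 4.9.2 is the one that feeds the endpoint in 5.2.3, and that the month-12 scan is read with its date visible. A reader might go further and conclude that the MRI result will be biased, or that MRI is the only endpoint that could be freed from expectation. Neither is shown: the first would need evidence on how the readings are made, and for ROM the plan does not even name the assessor. The primary endpoint, sample size and stated power are unaffected.

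**What to change.** Add to section 4.9.2, with a cross-reference in 5.2.3:

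> *At study end the Principal Investigator re-reads both scans of every patient from PACS, in random order, with date and patient code hidden, and scores each on the same cuff-integrity grade. These masked readings are used for the cuff-integrity endpoint. The unmasked day-0 reading is used for eligibility only.*

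Two details are needed for this to work. Baseline scans supplied by patients must be loaded to PACS. The cuff-integrity grade must be named before the re-read, since the plan gives none for this endpoint.

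**Cost.** Up to 48 extra readings by the same reader, and Data Manager time to hide dates and codes and to set the order. No extra scan, visit or reader is required.

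**Limits.** Masking may be partial: the investigator may recognise scans already used for enrolment, and differences in acquisition, above all for scans brought by patients, may reveal the time point. A reader not involved in enrolment would lessen recognition, at the price of an additional person. Neither version replaces a control group, so a change on MRI still could not be attributed to the device.
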